1.0 Objectives / Specific Aims

Assess feasibility of implementing the adapted SUPPORT-(D) intervention in up to 30 individuals living with Alzheimer's disease (PWD)/caregiver (CG) dyads in terms of recruitment, use and acceptability of the intervention, data collection methods, and obtain estimates of variability for outcome measures (e.g., QoL, acceptability, feasibility, safety, symptom burden, knowledge) to be used in the design of a subsequent adequately powered randomized control trial (RCT).

2.0 Background

Severity of the problem. It is estimated that over 11 million Americans are providing unpaid care to persons with dementia (PWD).¹ In 2021, Alzheimer's and other related dementias are estimated to cost the nation \$355 billion dollars. This is projected to increase to \$1.1 trillion dollars by 2050.¹ Dementia is a progressive, irreversible condition defined as an acquired loss of cognition in multiple cognitive domains sufficiently severe to affect social or occupational function.² Primary treatment goals for this chronic condition are to decrease suffering caused by cognitive and behavioral changes and delay inevitable progressive decline.² Healthcare utilization and costs are significantly higher in persons living with dementia compared to a demographically matched cohort.³ This population experiences a higher burden of comorbid physical disease, polypharmacy⁴ and, in advanced stages, challenges with independent mobility, increasing falls risk.⁵

The unpredictable and often extended illness trajectory coupled with progressive decreases in cognitive functioning creates a complex environment for symptom self-management often requiring family caregiver assistance. Caregivers (CG) of PWD report needing support to manage stress related to caregiving responsibilities, identifying respite care, building a network of support, and managing behavioral symptoms.⁶ Many PWD/CG dyads experience unmet needs which vary based on severity of cognitive impairment of the PWD.^{6,7} PWD and their CGs could benefit from interventions for improving early access to palliative care.⁸

Palliative care uptake among PWD remains limited. Despite a recent increase in hospice enrollments for PWD (fewer than 1% in 1995, to 18% in 2017), challenges remain with palliative care, in particular, advance care planning (ACP).⁹ Caregiver education regarding prognosis of dementia and ACP is limited.^{10,11} Initiation of palliative care among PWD is inhibited by the inability to verbalize preferences due to illness progression coupled with an often lengthy end of life phase.¹² While debate regarding the timing of the initiation of palliative care continues, ACP exists as a key milestone in care. Several possible triggers for engaging in ACP conversations include time of diagnosis, changes in care setting, changes in health status of the CG, or completion of a Lasting Power of Attorney.¹³ Advance care planning as part of the palliative care model can reduce caregiver burden and stress.¹⁴ Early ACP prior to the onset of severe cognitive impairment promotes care delivery consistent with the desires of PWD/CG and minimizes caregiver burden and stress during the end of life phase of the illness.

PWD/CG dyads face serious stressors. Evidence suggests dyadic interventions versus those that focus on solely on the individual can improve mutual understanding, communication and relationship quality among PWD/CG dyads and may have broader implications for positive health outcomes in the pair, such as reducing stress.¹⁵ Commonly reported stressors for PWD include intense negative emotions and distress, challenges obtaining accurate and helpful information, difficulty understanding diagnosis and disease trajectory, and a sense of loss of anticipated future.¹⁶ Additional stressors reported by PWD included experiences of loss, changes in relationship dynamics, living with the symptoms of dementia, learning to do things differently and establishing coping mechanisms.¹⁷ In contrast, CG report stressors associated with personal care, housekeeping, medication administration, financial responsibilities, and difficulty maintaining professional and social connections.¹⁸ Concerns for safety of the PWD were also reported by CGs.⁶ While some interventions exist to address stressors for the PWD/CG dyad, comprehensive interventions addressing most or all stressors are limited. Palliative care interventions to improve PWD/CG quality of life and safety while reducing caregiver burden are necessary.

Safety is an overlooked component of dementia care. Caregivers of PWD seek to prevent harm in four primary areas including physical harm, economic harm, emotional harm and relational harm.¹⁹ Evidence suggests 90% of community dwelling PWD have unmet safety needs, specifically related to falls risk, wander risk management and home safety evaluation.⁷ A recent systematic review of interventions for family caregivers of PWD identified 16 psychotherapeutic or psychoeducational interventions of which only 2 incorporated content related to providing a safe environment for PWD.²⁰ Martindale-Adams²¹ (2013) included a telephone delivered program with information related to safety and Pahlavanzade²² (2010) incorporated a lecture and group discussion on safety measures at home. However, outcome measures for PWD safety were not measured for either study; additionally, only one of these studies was conducted within the United States. Thus, additional research is necessary to better understand the impact of including safety as part of a palliative care intervention for PWD/CG dyads.

3.0 Intervention to be studied (A Program of SUPPORT-D)

This protocol describes the second phase of the study in which the SUPPORT-D intervention will be delivered to up to 30 PWD/CG dyads over six weeks. The SUPPORT-D intervention consists educational materials will be presented in a format with enhanced content (face-to-face virtually delivered by nurse interventionist via telehealth (e.g., MS Teams), with printed booklet, and identical digital content (electronic pdf and recorded videos of printed content). The SUPPORT-D intervention will be addressed in four sequential sections including: 1) understanding the disease 2) caring for myself; 3) information for the caregiver; and 4) planning for the future. Within the four sections of the intervention seven topics are addressed included symptom management, understanding your disease, putting safety first, ongoing conversations, respite care, palliative care, and alternative treatments. Included content for each SUPPORT-D is described in **Table 1**. The intervention contents are assembled in a bound printed book and recorded for viewing on a mobile device (tablet or smartphone) along with a pdf version of the booklet for easy reference.

4.0 Study Endpoints

Study end points include successful study completions, consent withdrawals, PI terminations, Lost contact with the patient, and unexpected adverse events.

Table 1. Included content for A Program of SUPPORT™-D

Intervention Component	Current Topics	Included content
Part 1. Understanding the disease	Symptom Management	Define dementia, discuss causes of dementia, describe what happens in the brain with dementia, discuss diagnostic tests and monitoring
	Understanding your disease	Discuss disease trajectory mild, moderate, and severe, enhancing self-management based on dementia severity, commonly asked questions, common medications, support groups
Part 2. Caring for myself	Putting safety first	Discuss how dementia affects safety, home safety tips including falls prevention, risks for wandering and mitigation strategies, what to do if wandering occurs
Part 3. Caring for your caregiver	Ongoing conversations	Discuss strategies for self-care, asking for help, and avoiding burnout, finding local resources, online tools for communication, safety strategies for caregivers , commonly asked questions
	Respite care	Define respite care and provide respite care resources
Part 4. Plan for the future	Palliative care	Discuss informing family and friends of diagnosis, considerations for moving forward (new/evolving treatments, advanced treatments, research participation, future care considerations), overview of palliative care, differences between palliative care and hospice, preparing for the end of life and making future care decisions
Part 4. Plan for the future	Alternative Treatments	Discuss herbal remedies, dietary supplements (e.g., Coenzyme Q10, Omega-3 fatty acids), concerns about alternative therapies

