Measures. Self-report and proxy assessments will be completed by PWD, and CG utilizing participant personal mobile device or provided tablet to electronically answer the study measures directly into REDCap or asked verbally by the PI or PC. Measures of knowledge, acceptability, feasibility, stress, symptom burden, quality of life, disease preparedness, safety, technology literacy and advanced care planning will be collected from PWD/CG dyads. Specific instruments, scoring and psychometric properties are described within Table 2. The PI or PC will be present during baseline and post-intervention data collection to answer questions but will be unobtrusive during data collection. The data will be stored in REDCap.

Statistical Analysis Plan: We will obtain multiple measures to assess feasibility and inform future efficacy and effectiveness trials. Variables pertaining to the study procedures and participant demographic variables will also be collected. Data to be collected is described within Table 2. Specifically, 95% confidence intervals for proportions will be used to estimate dichotomous outcomes including proportion of participants who agree to participate out of those approached, and the proportion adherent to the intervention protocol (i.e., attendance at all study visits). Frequency distributions, median and mean responses (with 95% confidence intervals) will be obtained for continuous feasibility measures (e.g., time spent using SUPPORT materials between study visits, number of times SUPPORT content shared with others) as well as measure of practicability (e.g., number of calls for assistance, inability to access telehealth meeting software, number of chat messages received for intervention content related questions). Qualitative data gathered from post-intervention key informant interviews will be analyzed using directed content analysis.³⁴

Outcome measures and estimates of preliminary impacts: Measures of central tendency (mean, median), variability and frequency distributions as appropriate will be used to analyze demographic and clinical characteristics. Variability estimates of changes from baseline to post intervention for knowledge, quality of life, symptom burden, stress, and safety with 95% confidence intervals (without p-values) will be provided.

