13.0 Provisions to Monitor the Data to Ensure the Safety of Subjects

The PI, [name] will be responsible for the overall monitoring of the safety of the study and the Program Coordinator (PC) [name] will be responsible for the daily monitoring and safeguarding of study data to ensure the safety and protection of all human study participants. [name] will report observed and solicited adverse events, and protocol deviations to [name]. [name] will be responsible for the classification of all reported adverse events (AE) and for ensuring that all serious adverse events (SAE), protocol deviations, and 'other' reportable events are forwarded to MUSC IRB in compliance with institutional policies and procedures. [name] will also be responsible for maintaining the electronic

regulatory binder, ensuring data management validation and verification of the electronic study research database.

Monitoring Study Safety. From initial screening of study participants utilizing inclusion and exclusion criteria; to the informed consent process; to intervention delivery; to training in Good Clinical practices (GCP) and regulations pertaining to the Conduct of Human Participant Research for study personnel; to routinely scheduled study contact with enrolled participants; to protocol fidelity monitoring; to the real time review of AEs; and oversight of MUSC's IRB-procedures for examining study safety are consistently afforded throughout the study. Specific procedures include:

- Participant screening using established inclusion/exclusion criteria per the protocol.
- Full disclosure of all known risks and the possibility of risk from study participation to participants during the informed consent process. Note these risks are minimal.
- Participants will be informed to notify the researchers of any/all suspected or experienced adverse events whether the event is believed to be related or not to the intervention.
- PI or PC will track all reported AE through to resolution.
- All members of the research team will maintain CITI and GCP training.
- PI or PC will maintain weekly contact with all participants to enquire about AE's, monitor study progress, compliance, and safety.
- Participant study logs will be reviewed by the PI or PC to monitor for fidelity compliance with the intervention.

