15.0 Risks to Subjects

We do not anticipate any significant risks related to participation in survey completion, or post intervention interviews. However, as with all studies, there are inherent risks involved with the conduct of human subject research that gathers Protected Health Information (PHI). Participants will be made aware of these risks during the Informed Consent process. Identified study risks include: Loss of privacy, emotional distress, and physical discomfort

Loss of privacy: PHI from participants will be gathered and stored electronically on secure and encrypted servers and there are risks associated for the loss of privacy and confidentiality. We will further minimize the potential for loss of confidentiality through the physical separation of participant names from their research record according to the process described above. Audio recordings of participants interviews will be uploaded for transcription within 48 hours to an outside agency with which MUSC has established a Business Associates Agreement (BAA). Once uploaded, all audio recordings will be deleted from the portable storage device.

Emotional distress: Some of the questions asked may be upsetting to participants or make them feel uncomfortable answering them. Participants will be instructed that if they do not wish to answer a question, they can skip it and go to the next question. In the rare and unexpected event of serious or life-threatening levels of distress, participants will be instructed to call 911 and/or visit the closest Emergency Department. In the event the caregiver expresses concern for the person living with Alzheimer's disease they will be referred to their primary care physician.

Physical fatigue: Completion of the sessions, questionnaire, measures and interviews may be tiring to some participants. Participants will be given ample time to complete the questionnaire and may take breaks as necessary throughout all study procedures.

In the rare and unexpected event of serious or life-threatening levels of distress, participants will be instructed to call 911 and/or visit the closest Emergency Department. In the event the caregiver expresses concern for the person living with Alzheimer's disease they will be referred to their primary care physician.

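### Section 4.0 counts only undefined unexpected adverse events, and neither Table 2 nor the SAP summarises the adverse events that Section 13.0 collects

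*Combined protocol and SAP*

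**What the plan says.** - **Endpoint (Section 4.0).** The list opens with the word include, names study completions, withdrawn consents and terminations by the PI, and ends with "Lost contact with the patient, and unexpected adverse events". No other adverse-event endpoint appears in the protocol, and the word unexpected is not defined.
- **Foreseen risks (Section 15.0).** "Identified study risks include: Loss of privacy, emotional distress, and physical discomfort". The text below that sentence adds "Physical fatigue: Completion of the sessions, questionnaire, measures and interviews may be tiring to some participants". The same section introduces its instruction on severe distress with "In the rare and unexpected event of serious or life-threatening levels of distress".
- **Collection (Section 13.0).** "Participants will be informed to notify the researchers of any/all suspected or experienced adverse events", whether or not they are thought to be related to the intervention. The PI or program coordinator asks about adverse events at weekly contacts and follows each one until it resolves, and responsibility for classifying them is assigned. Privacy breaches have a reporting route of their own in the same section.
- **Analysis (Section 10.0).** The SAP refers to Table 2 for the data to be collected. Table 2 has no adverse-event row. Its Safety row is the Safety Assessment Scale, completed by the caregiver at baseline and post-intervention. The matching analysis is "Variability estimates of changes from baseline to post intervention for knowledge, quality of life, symptom burden, stress, and safety", with 95% confidence intervals. The SAP has no line for adverse events, expected or unexpected.

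**The concern.** The protocol foresees certain harms, arranges to hear about them every week, and then names an endpoint whose wording leaves out the ones it foresaw. The SAP does not bring them back.

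This matters because the study exists to inform a later randomised trial, and Section 1.0 lists safety among the outcomes for which estimates are wanted. The intervention includes end-of-life content and the assessments are long, so transient distress and tiredness are the effects the planners of that trial would most want counted. If the plan is followed as written, the report could describe no adverse-event endpoint while the weekly contacts had recorded several such episodes. With the key word undefined, two members of staff could also count the same fall differently.

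**Working it through.** No figure in the documents bears on the scope of the endpoint, so there is nothing to reproduce. The check is a comparison of sections, followed by a short calculation of what a full summary would offer.

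**1. Which events the Section 4.0 wording reaches**

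| Event | Where the protocol mentions it | Counted by the Section 4.0 wording? |
|---|---|---|
| Non-serious emotional distress | Foreseen risk, Section 15.0 | No, on an ordinary reading |
| Physical discomfort or fatigue | Foreseen risk, Section 15.0 | No, on an ordinary reading |
| Serious or life-threatening distress | Section 15.0, itself called unexpected | Yes |
| Privacy breach | Foreseen risk, Section 15.0; separate reporting route, Section 13.0 | Probably not, but reported elsewhere |
| Fall or wandering | Section 2.0 and Table 1; not among the Section 15.0 risks | Unclear without a definition |

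On the last row, Section 2.0 cites evidence that "90% of community dwelling PWD have unmet safety needs, specifically related to falls risk, wander risk management and home safety evaluation", and Table 1 teaches prevention of both. A reader who relies on that would call such events expected. A reader who relies on the Section 15.0 list would call them unexpected.

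**2. Whether another planned output counts harms**

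- Safety Assessment Scale: a caregiver-completed score at two times, analysed as change.
- PSS: a summed stress score at the same two times, not named as an adverse-event measure.
- PROMIS-29: includes anxiety, depression and fatigue at the same two times, from PWD only if able.

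A mean change between baseline and week 8 does not show how many people became distressed or exhausted along the way. None of the three substitutes for a count.

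**3. What a full summary could show**

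Input: up to 30 PWD and up to 30 caregivers (Section 6.0). With no participant having an event, the exact two-sided 95% upper limit is 1 − 0.025^(1/n). For n = 30 this is 1 − 0.025^(1/30) = 0.1157, or 11.6%.

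The documents give no event rate, so the rates below are assumptions shown as a range. The chance of seeing at least one participant with an event is 1 − (1 − p)^30:

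| Assumed true proportion p | Expected number of 30 | Chance of at least one |
|---|---|---|
| 5% | 1.5 | 78.5% |
| 10% | 3 | 95.8% |
| 20% | 6 | 99.9% |

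If 3 of 30 had an event, the exact 95% interval would be 2.1% to 26.5%; if 6 of 30, 7.7% to 38.6%. These intervals are wide but usable for planning. Keeping PWD and caregivers separate also avoids treating the two members of a dyad as independent.

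**The case against.** The strongest reply is that Section 4.0 is not an outcome list at all. It reads as participant disposition, it opens with the word include, and it omits quality of life, knowledge, acceptability and symptom burden, all of which are planned outcomes. Absence from it therefore need not mean absence from the report. All events are solicited and followed up, adverse events are a standing item at team meetings (Section 12.0), and this is a single-arm educational study whose stated risks are minimal.

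Much of this is right, and it limits the point. It rules out several stronger readings that a reader might infer:

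- **That the study has no other safety outcome.** It has one, the Safety Assessment Scale, with a planned analysis.
- **That every named risk falls outside the endpoint.** Serious distress is itself called unexpected, and privacy breaches are reported by another route.
- **That falls and wandering are excluded.** They are not among the Section 15.0 risks. Section 2.0 speaks of unmet needs, not of how often the events occur, and it ties rising falls risk to advanced stages, whereas eligibility is FAST score ≤4. Their exclusion would be an inference.
- **That expected events are thrown away.** Nothing says so. The data will exist.

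Without a comparator, event proportions cannot show that the intervention caused or prevented harm. That does not make them useless for planning.

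What the reply does not meet is this: the one adverse-event endpoint carries an explicit restriction, the restriction is undefined, and no other part of the plan says that any adverse event will be summarised. Even the restricted endpoint has no analysis line.

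**Conclusion.** The point holds as a gap in reporting and analysis; it is not a failure of safety surveillance. As written, the adverse-event endpoint leaves out non-serious distress and discomfort or fatigue, leaves falls and wandering undecided, and has no planned summary. It should be changed, because the remedy is cheap and serves the study's stated purpose.

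This rests on reading unexpected in its ordinary sense, as not among the risks the protocol foresees. A written definition could alter that reading, but it would not supply the missing summary. The number of events affected cannot be estimated from the documents. The 11.6% upper limit assumes the full 30 in a group and would be higher with fewer.

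**What to change.** - **Section 4.0:** replace unexpected adverse events with all adverse events, classified by seriousness, relatedness and expectedness. Define expected by reference to the risks in Section 15.0. Under that definition a fall or wandering episode counts as unexpected unless it is added to the list; either way it enters the table.
- **SAP (Section 10.0):** add one line giving the number and proportion of PWD, and separately of caregivers, with at least one adverse event, with exact 95% CIs and a breakdown by the three classifications. Use as denominators those enrolled in each group, since Section 6.0 lets dyad members take part singly.

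No new contacts or instruments are needed: the weekly enquiries in Section 13.0 supply the events. That section assigns classification without stating the categories, so the adverse-event form should carry the three fields if it does not already. A compulsory prompt list of specific events is not required; it would be new solicitation. The cost is one extra descriptive table and a reported event count that looks less favourable.
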